7.4.1.3. Nonrelapse Mortality Rate Using Kaplan-Meier Approach

The survival distribution of NRM in each treatment group overall [REDACTED] will be estimated using the KM method, and the KM curves; medians; 1-, 2-, 3-, 6-, 9-, 12-, 18-, and 24-month survival estimates; and 95% CIs will be presented (Brookmeyer and Crowley 1982).

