#### 9.4.2. Secondary Analyses

The key secondary endpoint is NRM at Month 6, defined as the proportion of subjects who died due to causes other than malignancy relapse at Month 6. The comparison of NRM at Month 6 between treatment cohorts will be conducted using a 2-sample proportion test with normal approximation. Summary statistics and 95% CI will be provided.

Additional secondary endpoints will be analyzed as follows:

- ORR, defined as the proportion of subjects demonstrating a CR, VGPR, or PR at Days 14, 56, and 100. The comparison between treatment cohorts will be conducted using a 2-sample proportion test with normal approximation. Summary statistics and applicable 95% CI will be provided.
- NRM, defined as the proportion of subjects who died due to causes other than malignancy relapse at Months 9, 12, and 24. The comparison between treatment cohorts will be conducted using a 2-sample proportion test with normal approximation. Cumulative incidence rates will be provided. Summary statistics and applicable 95% CI will be provided.
- DOR, defined as the time from first response until GVHD progression or death. The comparison between treatment cohorts will be conducted using the log-rank test. The Kaplan-Meier method will be used. Summary statistics will be provided.
- TTR, defined as the interval from treatment initiation to first response.
- Relapse rate of malignant and nonmalignant hematologic diseases, defined as the proportion of subjects whose underlying disease relapses. The comparison between treatment cohorts will be conducted using a 2-sample proportion test with normal approximation. The cumulative incidence rate and summary statistics will be provided.

- Relapse-related mortality rate, defined as the proportion of subjects whose malignancy relapses and has a fatal outcome. The comparison between treatment cohorts will be conducted using a 2-sample proportion test with normal approximation. The cumulative incidence rate and summary statistics will be provided.
- FFS, defined as the proportion of subjects who are still alive, have not relapsed, have not required additional therapy for aGVHD, and have not demonstrated signs or symptoms of cGVHD, at Month 6. The comparison between treatment cohorts will be conducted using the log-rank test. The Kaplan-Meier method will be used. Summary statistics will be provided.

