7.1. General Considerations

In all efficacy analyses, initiation of new, systemic anti-GVHD therapy includes 2 scenarios:

1) initiation of new anti-GVHD therapy including a higher dose of corticosteroid than that used at Day 1 and 2) initiation of new, systemic anti-GVHD therapy when subjects who were treated with placebo in the treatment phase were re-treated with itacitinib in the retreatment phase.

Initiation of new, systemic anti-GVHD therapy will be considered when defining the following:

1) onset of response and 2) loss of response. When defining responder for Day 28 ORR; overall response at Days 14, 56, 100, and 180; and BOR, the onset of response will be censored by initiation of new, systemic anti-GVHD therapy. Responders who did not have GVHD progression or death after response will be censored at the time of either study withdrawal, initiation of new, systemic anti-GVHD therapy, or the date of last assessment of GVHD before or on the cutoff date, whichever is earliest. In the survival analysis of NRM, all subjects in the analysis set in question without a death due to causes other than malignancy relapse will be censored at either study withdrawal, death due to malignancy relapse, or the date of last contact before or on the cutoff date, whichever is earliest.

Duration of response will be calculated for every subject who has a response in the study; DOR will also be summarized for any subgroups of interest.

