$\widehat{CDF}_{pbo,j}(t = D180)$ and $SE(\widehat{CDF}_{pbo,j}(t = D180))^2$ are the cumulative distribution function estimate at Day 180 in the placebo group in the jth stratum and its variance, respectively.

$\widehat{CDF}_{trt,j}(t = D180)$ and $SE(\widehat{CDF}_{trt,j}(t = D180))^2$ are defined similarly in the itacitinib group for jth stratum subjects. $TS_{Day180NRM}$ will be asymptotically distributed as a Chi-square test statistic with degree of freedom equal to 1.

The overall estimate of treatment difference in Day 180 NRM between placebo and itacitinib is thus defined as the following:

$$w * [\widehat{CDF}_{pbo,standard}(t = D180) - \widehat{CDF}_{trt,standard}(t = D180)] + (1 - w) * [\widehat{CDF}_{pbo,high}(t = D180) - \widehat{CDF}_{trt,high}(t = D180)]$$

Its 95% CI is the above estimate of difference

$$\pm 1.96 * \sqrt{w^2 * (SE(\widehat{CDF}_{pbo,standard}(t = D180)))^2 + (SE(\widehat{CDF}_{trt,standard}(t = D180)))^2 + (1 - w)^2 * (SE(\widehat{CDF}_{pbo,high}(t = D180)))^2 + SE(\widehat{CDF}_{trt,high}(t = D180))^2)}$$

with weight w defined by inverse of variance in two baseline GVHD risk groups. That is:

$$w = \frac{1/[SE(\widehat{CDF}_{pbo,standard}(t=D180))^2 + SE(\widehat{CDF}_{trt,standard}(t=D180))^2]}{1/[SE(\widehat{CDF}_{pbo,standard}(t=D180))^2 + SE(\widehat{CDF}_{trt,standard}(t=D180))^2] + 1/[SE(\widehat{CDF}_{pbo,high}(t=D180))^2 + SE(\widehat{CDF}_{trt,high}(t=D180))^2]}$$

In order to conduct above hypothesis testing for NRM at Day 180, time to NRM, defined as the interval between randomization and death due to causes other than malignancy relapse, will be derived. All subjects in the FAS without a death due to causes other than malignancy relapse will be censored at either study withdrawal, death due to malignancy relapse, or the date of last contact before or on the cutoff date, whichever is earliest.

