In subdistribution hazard modeling, competing-risk events will be considered to remain in the risk set as described by Gray (1988). Stratified Gray's test [REDACTED] will be used to test equality of 2 cumulative incidence curves. Cumulative incidence function at Day 180 (SE) will be estimated. Stratified subdistribution hazard regression (Fine and Gray 1999) with cofactor of treatment group (itacitinib vs placebo) will be performed, and subdistribution hazard ratio (95% CI) on treatment effect (itacitinib vs placebo) will be estimated.

Cumulative incidence curve for each competing-risk analysis will be plotted overall by Day 28 response status [REDACTED]

7.4.4. Overall Response Rate at Days 14, 56, 100, and 180

Similar to Day 28 ORR, ORR at Days 14, 56, 100, and 180, respectively, is defined as the proportion of subjects demonstrating a CR, VGPR, or PR at a defined analysis visit/window (ie, ± 3 days of scheduled visit date).

The ORR on Days 14, 56, 100, and 180 will be estimated with a 95% CI. The proportion of responders will be estimated with 95% CIs. Confidence intervals will be calculated based on the exact method for binomial distributions. Summary statistics will be provided.

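### NRM at Months 9, 12 and 24: the readable SAP gives numeric estimates only by Kaplan-Meier with relapse deaths censored, not the cumulative incidence the Protocol promised

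*SAP*

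**What the plan says.** Protocol section 2 and SAP Table 1 both list NRM at Months 9, 12 and 24 as a secondary endpoint. Protocol 9.4.2 defines it as the proportion of subjects dead from causes other than relapse at those months. It plans a two-sample proportion test and adds "Cumulative incidence rates will be provided".

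The SAP handles time to NRM in two places:

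- **Kaplan-Meier.** Under 7.4.1.3 the distribution in each arm "will be estimated using the KM method, and the KM curves; medians; 1-, 2-, 3-, 6-, 9-, 12-, 18-, and 24-month survival estimates", with 95% CIs. Under 7.1, subjects without a non-relapse death "will be censored at either study withdrawal, death due to malignancy relapse, or the date of last contact before or on the cutoff date". Section 7.4.1.2 repeats that rule.
- **Competing risks.** Section 7.4.3 sets out two analyses, one with relapse and one with relapse death as the competing event. Each has a stratified Gray's test, which "will be used to test equality of 2 cumulative incidence curves", and a stratified Fine-Gray regression. On estimates it says "Cumulative incidence function at Day 180 (SE) will be estimated", and on graphs "Cumulative incidence curve for each competing-risk analysis will be plotted overall by Day 28 response status".

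SAP 10.1, which records departures from the Protocol's analyses, contains only a note on the naming of the full analysis set.

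**The concern.** A subject who dies of relapse can no longer die a non-relapse death. Censoring that subject in a Kaplan-Meier analysis treats the subject as still able to have the event later. One minus KM then describes NRM in a hypothetical setting without relapse deaths, whereas the endpoint is the proportion of randomized subjects who actually die of other causes.

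The SAP recognizes the issue. Section 7.4.3 calls competing risks the usual setting for NRM, and Appendix A concedes that the log-rank, KM and Cox methods leave competing risk out. Yet the one time with a numeric cumulative incidence is Day 180, the earliest of the NRM landmarks and the one where the two estimators differ least.

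At stake are the figures that would be read as the results for three named secondary endpoints. If the SAP is followed as written, they would be too high in each arm and would not be the quantity that the Protocol defines.

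**Working it through.** **1. Plan figures used.** The documents give no NRM figure after Month 6. Protocol 9.2 gives Day 180 rates of 33% (control) and 19.8% (itacitinib), with 207 per arm and 83% power. With the stated strata (22% and 44% against 12.4% and 28.2%, split 50:50, 1-sided 0.025), a two-stratum CMH approximation gives 82.2% power with continuity correction and 85.1% without. The inputs are therefore read as intended.

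**2. Direction within an arm.** Let λ(t) be the NRM hazard and μ(t) the relapse-death hazard, with S_N = exp(−∫λ) and S_R = exp(−∫μ). One minus KM grows at rate λ·S_N. The cumulative incidence (CIF) grows at rate λ·S_N·S_R. The gap therefore grows at rate λ·S_N·(1 − S_R), which is never negative. One minus KM is at or above the CIF in each arm, and the gap cannot shrink.

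**3. Size, narrower assumptions.** Assumed: one minus KM at Day 180 equal to 33% and 19.8%, NRM hazard falling to a quarter after Month 6, constant relapse-death hazard μ, and relapse-death incidence by Month 24 of 15% or 25% in each arm.

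Monthly hazards to Month 6 are λ1 = −ln(0.67)/6 = 0.4005/6 = 0.06675 for placebo and −ln(0.802)/6 = 0.2206/6 = 0.03677 for itacitinib. The cumulative hazard at Month 24 is the Month 6 value times 1 + (18/6)(0.25) = 1.75. So one minus KM at Month 24 is

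- placebo: 1 − exp(−0.4005 × 1.75) = 50.4%
- itacitinib: 1 − exp(−0.2206 × 1.75) = 32.0%

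For t above 6, with λ2 = λ1/4,

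CIF(t) = λ1/(λ1+μ)·[1 − e^(−6(λ1+μ))] + e^(−6(λ1+μ))·λ2/(λ2+μ)·[1 − e^(−(t−6)(λ2+μ))].

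The value of μ is solved so that relapse-death incidence at Month 24 meets the assumption. For placebo at 25%, μ = 0.01999 and CIF(24) = 0.7695 × 0.4057 + 0.5943 × 0.4550 × 0.4832 = 0.312 + 0.131 = 44.3%.

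| Relapse deaths by Month 24 | Arm | 1 − KM | CIF | Excess (points) |
|---|---|---|---|---|
| 15% | placebo | 50.4% | 46.9% | 3.5 |
| 15% | itacitinib | 32.0% | 30.0% | 2.0 |
| 25% | placebo | 50.4% | 44.3% | 6.1 |
| 25% | itacitinib | 32.0% | 28.6% | 3.4 |

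At Month 9 the excess is 1.2 to 2.2 points (placebo) and 0.6 to 1.1 (itacitinib). From unrounded values, the Month 24 arm difference is 18.4 points by KM against 16.8 (15%) or 15.7 (25%) by CIF.

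**4. Size, wider assumptions.** Here the CIF, not one minus KM, is fixed at 33% and 19.8% at Day 180. Relapse-death incidence at 12 months runs from 5% to 20%, and the NRM hazard after Month 6 from 0.3 to 1.0 times the earlier one. Entries are KM minus CIF, in points.

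| Quantity | Month 9 | Month 12 | Month 24 |
|---|---|---|---|
| Control arm, equal relapse mortality | 0.7 to 5.2 | 0.9 to 7.9 | 2.2 to 17.3 |
| Arm difference, equal relapse mortality | +0.3 to +2.4 | +0.4 to +3.3 | +0.9 to +4.7 |
| Arm difference, 10% control and 20% itacitinib | −0.3 to −0.4 | −0.4 to −0.9 | −1.1 to −3.9 |
| Arm difference, 20% control and 10% itacitinib | +2.5 to +3.9 | +3.2 to +5.7 | +6.5 to +11.1 |

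For example, with 10% control and 20% itacitinib relapse deaths and a late hazard of 0.3 at Month 24, KM gives 54.8% − 36.3% = 18.5 points and the CIF gives 50.3% − 30.7% = 19.6 points. KM then understates the difference by 1.1 points.

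**The case against.** The strongest reply is that the plan does not ignore the competing risk. The Protocol sentence on cumulative incidence has not been withdrawn, and SAP 7.4.3 tests and models whole incidence curves and plots them without a stated time limit. Section 7.4.1.3 is openly headed as a Kaplan-Meier approach and does not claim to replace the Protocol's proportion. This stands in part. A reader might infer that later NRM is analyzed by Kaplan-Meier alone, or that cumulative incidence is planned only at Day 180. The documents do not support that: only the numeric cumulative incidence is tied to Day 180. But a plotted curve is not an estimate with a confidence interval, and 7.4.1.3 is the only readable place that specifies one at these months.

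A reader might also infer that Kaplan-Meier must overstate the benefit of itacitinib. It need not. The sign depends on relapse mortality by arm, as the third row of the second table shows. Protocol 1.1 itself warns that measures against GVHD may increase relapse, so higher relapse mortality on itacitinib cannot be set aside.

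The magnitudes rest on assumed hazards, and the two sets of assumptions give quite different ranges. Parts of 7.4.1.3 and 7.4.3 are redacted, and the available planned-table list starts at Table 2.2.31. A cumulative incidence table at later months therefore cannot be excluded.

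Finally, SAP 3.2 applies no multiplicity control to these endpoints. A reader who sees a threat to the trial's main claims would be mistaken: the primary test, the key secondary test and the interim rules do not use these estimates.

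**Conclusion.** The point holds as a gap between Protocol and SAP with a known direction within each arm. In the readable text, the Protocol's cumulative incidence rates at Months 9, 12 and 24 are not carried into numeric estimates, its two-sample proportion test at those months is not carried over either, and no change is declared. The estimator that is specified exceeds the defined proportion in each arm whenever relapse deaths precede later non-relapse deaths, and most at Month 24.

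Under the narrower assumptions the Month 24 excess is about 2 to 6 points per arm. Under the wider ones it is about 2 to 17 points in the control arm. Neither range can be narrowed from the documents. No general statement about the arm difference is justified. This should be corrected before the later NRM results are reported, but it does not affect the confirmatory conclusions.

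**What to change.** In SAP 7.4.1.3 and 7.4.3, name the cumulative incidence of NRM with 95% CI, by arm, at Months 9, 12 and 24 as the reported NRM estimate. Take it from competing-risks analysis II, whose competing event is relapse death. That analysis matches the endpoint, which is defined by cause of death. Analysis I stops at relapse itself, so it would not count a later non-relapse death in a relapsed subject. Label the Kaplan-Meier values as supportive. If the Protocol's two-sample proportion test at these months is not to be run, record that in SAP 10.1. If a redacted or unavailable table already gives these values, a cross-reference in 7.4.1.3 is enough.

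The cost is a few extra table rows from an analysis already planned for Day 180. No new data are needed, and neither the sample size nor the alpha allocation changes.

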7.4.2. Survival Analyses of Nonrelapse Mortality

Time to death due to causes other than malignancy relapse (NRM) will be analyzed according to the randomized treatment group and strata assigned at randomization.

The hazard ratio of itacitinib relative to placebo overall [REDACTED] will be calculated, along with its 95% CI, using a stratified Cox model.

Stratified log-rank test will also be used to test survival curve of NRM in the treatment group relative to placebo group using the FAS.

Subgroup KM analyses of NRM will also be conducted by Day 28 response status [REDACTED].

7.4.3. Competing-Risks Analyses of Nonrelapse Mortality

In the literature, analyzing NRM is normally conducted in the context of a competing-risks situation. Time from randomization to first occurrence of NRM or competing event is observed and used for analysis; otherwise, the subject is censored. Nonrelapse mortality and a competing-risk event are mutually exclusive. This is because a subject either dies due to malignancy relapse, dies due to an event other than malignancy relapse, or is censored at last follow-up. There are 2 types of competing-risks analyses:

- I: Time to NRM competing with time to malignancy relapse
Time to first occurrence of either death due to reasons other than malignancy relapse (NRM) or malignancy relapse is defined as an event of interest and competing risk event, respectively. Subjects without an event (neither event of interest nor competing event) will be censored at the date of study withdrawal or date of last contact before or on the cutoff date, whichever is the earlier.
- II: Time to NRM competing with time to death due to malignancy relapse
Time to first occurrence of either death due to reasons other than malignancy relapse (NRM) or death due to malignancy relapse is defined as an event of interest and competing risk event, respectively. Subjects without an event (neither event of interest nor competing event) will be censored at the date of study withdrawal or date of last contact before or on the cutoff date, whichever is the earlier.

For each of the competing-risks analyses (ie, I and II), there are 2 ways of modeling conducted in this study. The first one is cause-specific hazard modeling and the second one is subdistribution hazard modeling.

In cause-specific hazard modeling, competing events will be censored, and a stratified log-rank test [REDACTED] will be used to test 2 KM curves with KMC estimate equals 1 minus KM estimate. In cause-specific hazard modeling, stratified Cox regression model [REDACTED] with a cofactor of treatment group will be used to estimate cause-specific hazard ratio (itacitinib vs placebo) and 95% CI.

In subdistribution hazard modeling, competing-risk events will be considered to remain in the risk set as described by Gray (1988). Stratified Gray's test [REDACTED] will be used to test equality of 2 cumulative incidence curves. Cumulative incidence function at Day 180 (SE) will be estimated. Stratified subdistribution hazard regression (Fine and Gray 1999) with cofactor of treatment group (itacitinib vs placebo) will be performed, and subdistribution hazard ratio (95% CI) on treatment effect (itacitinib vs placebo) will be estimated.

Cumulative incidence curve for each competing-risk analysis will be plotted overall by Day 28 response status [REDACTED]

7.4.4. Overall Response Rate at Days 14, 56, 100, and 180

Similar to Day 28 ORR, ORR at Days 14, 56, 100, and 180, respectively, is defined as the proportion of subjects demonstrating a CR, VGPR, or PR at a defined analysis visit/window (ie, ± 3 days of scheduled visit date).

The ORR on Days 14, 56, 100, and 180 will be estimated with a 95% CI. The proportion of responders will be estimated with 95% CIs. Confidence intervals will be calculated based on the exact method for binomial distributions. Summary statistics will be provided.

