## **4. INVESTIGATIONAL PLAN**

### **4.1. Overall Study Design**

This is a randomized, double-blind, placebo-controlled, multicenter Phase 3 study of itacitinib or placebo in combination with corticosteroids as first-line treatment of subjects with Grade II to IV aGVHD. Subjects will be randomized 1:1 to itacitinib 200 mg plus corticosteroids or matching placebo plus corticosteroids. Randomization will be stratified by GVHD risk status (ie, standard risk vs high risk; [MacMillan et al 2015](#); [Appendix C](#)). Subjects will receive randomized study treatment until treatment failure (progression of disease, no response, or requiring additional systemic therapy), unacceptable toxicity, or death. Transfusion support and continued use of anti-infective medications, GVHD prophylaxis medications (including calcineurin inhibitors), and topical steroid therapy are permitted.

GVHD staging and grading will be assessed for efficacy as per MAGIC criteria ([Harris et al 2016](#)); safety and tolerability will be assessed as per NCI CTCAE v4.03 ([NCI 2009](#)).

An independent DMC will perform a futility-only interim analysis for primary analysis on ORR at Day 28 once 112 subjects (56 per cohort) have completed the Day 28 visit or withdrew early

from the study. If the futility boundary is crossed, the sponsor will consider stopping the study for futility. Otherwise, a second interim analysis on ORR at Day 28 for primary analysis will be conducted for both efficacy and futility once 240 subjects have completed the Day 180 visit or withdrew early from the study. If neither the futility nor efficacy boundary is crossed, the study will continue to accrue approximately 436 subjects and then the final analysis for the primary analysis will be conducted using CMH test. The study will end once 75% of subjects have achieved 2-year transplant-related mortality, have died, or have been lost to follow-up.

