2.2. Study Objectives and Endpoints

[Table 1](#) presents the study objectives and endpoints.

Table 1: Objectives and Endpoints

Primary Objective	Primary Endpoint
Compare the efficacy of itacitinib in combination with corticosteroids versus placebo in combination with corticosteroids in terms of ORR at Day 28 in subjects with aGVHD.	ORR at Day 28, defined as the proportion of subjects demonstrating a CR, VGPR, or PR.
Key Secondary Objective	Key Secondary Endpoint
Compare the efficacy between treatment cohorts at a subsequent key clinical landmark.	NRM at Month 6, defined as the proportion of subjects who died due to causes other than malignancy relapse at Month 6.
Secondary Objectives	Secondary Endpoints
Compare additional response and longer-term efficacy outcomes between treatment cohorts.	ORR, defined as the proportion of subjects demonstrating a CR, VGPR, or PR at Days 14, 56, and 100.
	NRM at Months 9, 12, and 24.
	DOR for responders will be calculated. The DOR is defined from the time of the onset of response to loss of response. Subjects who died or discontinued will be censored at the death date or the previous assessment.
	TTR, defined as the interval from treatment initiation to first response.
	Relapse rate of malignant and nonmalignant hematologic diseases, defined as the proportion of subjects whose underlying hematologic disease relapses.
	Malignancy relapse-related mortality rate, defined as the proportion of subjects whose malignancy relapses and has a fatal outcome.
	FFS, defined as the proportion of subjects who are still alive, have not relapsed, have not required additional therapy for aGVHD, and have not demonstrated signs or symptoms of cGVHD, at Month 6.
OS, defined as the interval from study enrollment to death due to any cause.	
Assess the incidence and severity of AEs and SAEs.	Clinical safety data (eg, AEs, infections) will be tabulated and listed.
Evaluate the PK of itacitinib when administered in combination with corticosteroids.	C_{max} , C_{min} , t_{max} , AUC, and CL/F.
Evaluate the incidence of secondary graft failure.	Incidence rate of secondary graft failure, defined as > 95% recipient cells any time after engraftment with no signs of relapse, OR retransplantation because of secondary neutropenia ($< 0.5 \times 10^9/L$) and/or thrombocytopenia ($< 20 \times 10^9/L$) within 2 months of transplant.

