3.3. Sample Size Considerations

A sample size of 414 subjects with 1:1 randomization (itacitinib vs placebo) and stratification based on baseline aGVHD risk status (standard risk vs high risk) provides approximately 90% power to test for the primary endpoint (ORR at Day 28) and approximately 80% power to test for the key secondary endpoint (NRM rate at Month 6). The family-wise α -level will be controlled at 0.025 overall for the two comparisons. Specifically, this study will claim to have achieved the efficacy objective when the primary endpoint ORR at Day 28 shows a significant treatment effect at 1-sided $\alpha = 0.025$. Conditional on significance of the primary endpoint, the key secondary endpoint (NRM rate at Month 6) will be tested at 1-sided $\alpha = 0.025$.

An absolute improvement of 16% in the primary endpoint of ORR at Day 28 would be considered a clinically meaningful improvement over standard first-line systemic treatment for aGVHD. A sample size of 414 subjects (207 subjects per treatment group) will provide approximately 90% power to detect a 16% overall difference (72% vs 56%) between treatment groups for the primary endpoint (ORR at Day 28) at a 1-sided alpha level of 0.025.

The assumed Day 28 ORR of 56% is based on MacMillan et al (2015). The stratum-specific response rates (standard risk, 68%; high risk, 44%) assume a standard risk:high risk ratio of 0.50:0.50. It is expected that treatment with itacitinib will result in a 16% increase in the ORR, that is, an expected odds ratio of 2.02 (which corresponds to an overall increase in ORR to 72%), with stratum-specific response rates of 81% and 61% for standard-risk and high-risk aGVHD cohorts, respectively. Power for the CMH test with stratification based on GVHD risk score was calculated using software N-Query 5.0.

[figure not shown]

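### SAP 7.4.4 names no between-arm comparison for ORR at Days 14, 56 and 100, Protocol 9.4.2 names an unstratified one, and nothing reconciles them (free improvement, low severity)

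*SAP*

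**What the plan says.** The objective attached to these endpoints (Protocol 2, SAP 2.2) is comparative: "Compare additional response and longer-term efficacy outcomes between treatment cohorts".

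SAP 7.4.4 defines ORR at Days 14, 56, 100 and 180 in the same way as Day 28 ORR. For the analysis it says only "The ORR on Days 14, 56, 100, and 180 will be estimated with a 95% CI" and "Confidence intervals will be calculated based on the exact method for binomial distributions", plus summary statistics. An exact binomial interval describes one proportion. The section names no difference, odds ratio or test.

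Protocol 9.4.2, for Days 14, 56 and 100, says "The comparison between treatment cohorts will be conducted using a 2-sample proportion test with normal approximation". It mentions no stratification. Protocol 9.3 sets a two-sided 0.05 level for analyses other than the primary and key secondary.

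On stratification, Protocol 4.1 says "Randomization will be stratified by GVHD risk status". SAP 3.3 treats that factor as strongly prognostic for Day 28 response: "The stratum-specific response rates (standard risk, 68%; high risk, 44%) assume a standard risk:high risk ratio of 0.50:0.50".

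The same endpoint at Day 28 (SAP 7.3.1.1) gets a stratified CMH p-value, a difference in proportions and an odds ratio with Wald limits. SAP 10.1, the section for changes to protocol-defined analyses, records only that the full analysis set equals the protocol's efficacy evaluable population.

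**The concern.** A programmer working from these documents has three candidate analyses for one set of secondary endpoints: separate intervals per arm with no comparison, the protocol's unstratified z-test, or a stratified CMH test borrowed from Appendix A. The choice should be fixed before unblinding, and the plan does not fix it.

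The one test that is expressly assigned to these days also fits the design less well than the Day 28 test does. When randomisation is stratified on a prognostic factor, the pooled variance of an unstratified test includes between-stratum variation that does not contribute to the error of the treatment difference. The test is then conservative and gives up some power. At stake are a clear link from protocol to SAP, consistency with Day 28, and a little efficiency. The validity of the trial's main claims is not at stake.

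**Working it through.** **Inputs.** Day 28 ORR by stratum, from SAP 3.3: control 68% and 44%, 50:50; itacitinib "with stratum-specific response rates of 81% and 61% for standard-risk and high-risk aGVHD cohorts, respectively". Evaluable sample 414 (207 per arm); randomised sample 436 (218 per arm). Two-sided 0.05 from Protocol 9.3, critical value 1.96. No rates are given for Days 14, 56 or 100, so the Day 28 rates are an assumption for those days.

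**Strength of the stratum.** Control odds ratio, standard v high risk: (0.68/0.32)/(0.44/0.56) = 2.70.

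**Step 1. Reproduce the plan's figure (Day 28, stratified CMH, 207 per arm, about 90%).**
- Difference: (0.81 + 0.61)/2 − (0.68 + 0.44)/2 = 0.71 − 0.56 = 0.15. The plan rounds this to 72% v 56%.
- True variance of the difference × n, with arms balanced within strata: (0.2176 + 0.2464 + 0.1539 + 0.2379)/2 = 0.4279. SE = √(0.4279/207) = 0.0455.
- Stratified null variance × n: 2 × (0.745×0.255 + 0.525×0.475)/2 = 0.4394. SE = √(0.4394/207) = 0.0461.
- Power = Φ[(0.15 − 1.96×0.0461)/0.0455] = 90.5%, or 88.6% with continuity correction. The stated 90% reproduces.

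**Step 2. Unstratified v stratified at 218 per arm.**
- True SE in both cases: √(0.4279/218) = 0.0443.
- Unstratified null SE: pooled rate 0.635, √(2×0.635×0.365/218) = 0.0461. Power = Φ[(0.15 − 1.96×0.0461)/0.0443] = 91.1%.
- Stratified null SE: √(0.4394/218) = 0.0449. Power = Φ[(0.15 − 1.96×0.0449)/0.0443] = 91.9%.
- Simulation (400,000 trials, arms balanced within strata): 91.3% unstratified, 91.9% CMH.

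**Step 3. Type I error of the unstratified test.** With control rates in both arms, the pooled variance is 2×0.56×0.44 = 0.4928 and the within-stratum variance is 0.2176 + 0.2464 = 0.4640. The effective critical value is 1.96×√(0.4928/0.4640) = 2.02, giving a two-sided level of about 0.043. Simulation gives 0.042, and 0.051 for CMH.

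**Step 4. Loss in subjects.** The right question is how many subjects the CMH test needs to match the unstratified power at 436. By simulation, CMH power at 424 subjects is about 91.2%, against 91.3% for the unstratified test at 436. The loss is 436 − 424 = about 12 subjects.

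**Step 5. Range (218 per arm, two-sided 0.05, common odds ratio 2.02).**

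| Control rates, standard/high risk | Power, unstratified | Power, CMH | Type I error, unstratified |
|---|---|---|---|
| 61% / 51% | 93.7% | 93.7% | 0.047 |
| 68% / 44% | 92.1% | 92.7% | 0.042 |
| 76% / 36% | 87.3% | 90.1% | 0.030 |

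The middle row differs slightly from step 2 because an exact odds ratio of 2.02 gives 81.1% and 61.3% rather than the plan's rounded rates. With smaller effects, where power is further from its ceiling, the loss stays within the same range: 57.5% v 59.8% for a 10-point effect in each stratum, and 74.3% v 76.0% for 12 points.

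**The case against.** **Appendix A may already supply the test.** Under its overall-response heading, SAP Appendix A describes a CMH test between arms and a logistic model with the stratification factor, and limits neither to Day 28. A reader of 7.4.4 alone might infer that the SAP contains no between-arm comparison for these days. The documents do not support that. The efficacy part of the Appendix B table list before Table 2.2.31 is also absent from the text available here, so a planned comparative table cannot be excluded. This part of the objection stands: the defect is ambiguity, not proven absence.

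The ambiguity remains, for three reasons. For Day 28 ORR, Month 6 NRM, FFS and OS, the SAP names the stratified test in the endpoint section itself, so silence in 7.4.4 reads as estimation only. Appendix A's hypothesis is one-sided, while Protocol 9.3 sets a two-sided level for these analyses. SAP 7.2 does list these days beside Day 28, but as a rule for choosing the assessment, and the hypotheses stated there concern Day 28.

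**The objective can still be met.** The protocol's comparison has not been withdrawn, and SAP 3.2 takes an estimation approach to endpoints outside the controlled family. This also stands. It would be too strong to say that the trial cannot compare the arms on these days.

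**The efficiency loss is minor.** This stands. The unstratified test is valid and errs conservatively, and these endpoints carry no confirmatory alpha.

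**Conclusion.** The point holds as a gap in specification with a small efficiency cost. SAP 7.4.4 assigns no comparison to endpoints whose objective is to compare, Protocol 9.4.2 assigns an unstratified test, it is unclear whether Appendix A applies, and SAP 10.1 does not reconcile them.

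On the Day 28 rates, the unstratified test runs at about 0.042 instead of 0.05 and has 91.3% power against 91.9%. This rests on carrying those rates to other days, a 50:50 risk mix and balance within strata. The loss is about 0 points at control rates of 61/51% and about 3 points at 76/36%.

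A reader might take the ratio of unstratified to stratified variance at the plan's rates, (0.56×0.44 + 0.71×0.29)/0.4279 = 0.4523/0.4279 = 1.057, and infer that some 25 of 436 subjects are wasted. That overstates the loss about twofold. With arms balanced within strata, both tests use the same difference with the same true sampling error, and only the critical value of the unstratified test is too strict. Nor is there any added false-positive risk.

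This is a free improvement of low severity.

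**What to change.** In SAP 7.4.4, state that the method of 7.3.1.1 applies to ORR at Days 14, 56 and 100: stratified CMH test with a nominal two-sided p-value, and stratified risk difference and odds ratio with 95% CIs. Keep the exact intervals per arm as description.

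In SAP 10.1, record that this replaces the unstratified 2-sample proportion test of Protocol 9.4.2 for these endpoints. In Appendix A, say which endpoints and days its CMH text covers.

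ORR at Day 180 appears in SAP 7.4.4 but is not among the endpoints listed in either document, so label it as additional.

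The cost is a few sentences in the SAP and a rerun of the Day 28 program on other visits. No new data and no protocol amendment are needed.
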